### **Consent Procedures**

## **IRB00003098 Funding Protocol rhBMP-2/ACS vs. Autograft for Critical Size Tibial Defects**

Written consent will be obtained during the clinic visit when bone graft surgery is scheduled. Prior to bone grafting procedure, female patients will be given a pregnancy test. Those with a positive pregnancy test will no longer be eligible and will receive standard treatment (iliac crest autograft). Patients with an active infection at the operative site, purulent drainage from the fracture or evidence of active osteomyelitis are not eligible for the study. Active infection will be defined clinically by skin changes, including redness, warmth and active drainage. Additionally, the diagnosis can be supported by laboratory values, including elevated WBC, ESR and CRP. Osteomyelitis is suspected by radiographic evidence of lytic lesions. If, at the time of surgery, the surgeon is concerned that the patient has a deep wound infection because of intra-operative findings that may include loose hardware, purulence or an inflammatory tissue reaction – the patient will be excluded from the study.

Informed consent will be obtained before any study procedures are initiated. The consent form will be reviewed in its entirety with the patient by the surgeon and research coordinator and all questions will be answered. Investigators will ask the subject questions to assure understanding before the consent for participation in the study is signed, specifically:

1. Can you explain what it means to be involved in this study?
2. What should you do if you no longer want to participate in the study?

If the patient cannot answer these questions, the patient will be deemed by the investigator to be incapable of providing informed consent secondary to a lack of mental competence; the subject will not be enrolled into the study.

### **Inclusion/Exculsion Criteria**

#### Criteria For Inclusion Of Subjects:

- Patients 18-65 years old with an open tibia fracture involving diaphysis (if patient has a bilateral tibia fracture and both require a bone graft, then each will be randomized separately).
- Tibia fractures with a circumferential bone defect of at least one centimeter in length compromising at least 50% of the circumference of the bone.
- The definitive treatment of the tibia fracture must be with an intramedullary nail (may have temporary external fixation prior to IM nail placement).
- Patients whose treatment plan includes placement of a bone graft between 6 to 16 weeks after their initial injury.
- Patients who have no evidence of infection by clinical examination (defined as active infection at the operative site, purulent drainage from the fracture or evidence of active osteomyelitis at the time of bone graft).
- Patients who are independent in living and ambulation prior to injury.
- Patients who are English speaking.
- Patients who are willing to provide consent and available for follow-up for at least 12 months following definitive surgical procedure.

Criteria For Exclusion Of Subjects:

- Patients who are pregnant or lactating.
- Patients with known hypersensitivity to rhBMP-2 or bovine type I collagen.
- Patients with a history of tumor, a resected or extant tumor, an active malignancy, or patients undergoing treatment for malignancy.
- Patients who are skeletally immature (<18 years of age or no radiographic evidence of epiphyseal closure).
- Patients with inadequate neurovascular status, e.g. high risk of amputation.
- Patients with compartment syndrome of the affected limb.
- Patients with immune deficiency or history of auto-immune disease,
- Patients who have undergone treatment of any other investigational therapy within the month preceding implantation or planned within the 12 months following implantation.
- Patients unable to return for required follow-up visits.
- Patients who have medical co-morbidities that preclude treatment with a general anesthetic.
- Patient who is pending incarceration or who is incarcerated.
- Patients with an active infection at the operative site defined clinically by skin changes including redness, warmth and active draining, purulent drainage from the fracture or evidence of active osteomyelitis based on radiographic evidence of lytic lesions at the time of bone grafting.
- Patient has segmental defects longer than 5cm in length as measured on AP and lateral radiographs of the injury taken after the final debridement following internal fixation
- Patient has a segmental defect longer than 6cm as measured intraoperatively after debriding .
- Patients who have segmental defects that require more than 60 cc of bone graft.
- Patients who require more than one large kit of rhBMP-2 at time of surgery.
- Patient's anticipated treatment plan also includes the use of other procedures to promote fracture healing, e.g. ultrasound, magnetic field or electrical stimulation.
- Patient's tibia fracture has been treated with additional fixation beyond the intramedullary nail, e.g. plates, wires or screws, and additional surgical fixation, e.g. fibulectomy, exchange nail and dynamization of locked nail
- Patients who have pathological fractures; a known history of Paget's disease or known history of heterotopic calcification.
- Patients with a Glasgow Coma Scale less than 15 (less than fully awake) at the time of informed consent.
- Patients with previous hardware in place that prevents placement of an intramedullary nail for treatment of the tibial shaft fracture.
- Patients with prior use of INFUSE.

*If the patient is a female of child bearing potential:*

- Does she have a negative pregnancy test (administered within 72 hours prior to surgery)?
- Has she agreed to use adequate contraception for a period of at least 1 year following implementation of rhBMP-2?

### **Number of Sites/Investigators/Patients**

There will be up to a total of twenty two (22) sites enrolling patients, all of which are familiar with randomized clinical trials and are part of the Major Extremity Research Consortium (METRC). Approval by each center's institutional review board will be obtained prior to commencing the study and we will follow the research guidelines set forth by each site. A total 50 patients will be enrolled in this study. The definitive treatment of the tibia fracture in all patients must be with an intramedullary nail. The number of patients enrolled at each site will be dependant on the random nature of the admission to hospital of eligible patients. No one site will enroll more than 10 patients in this study.

The randomization scheme is a central, computerized process using a web based, distributed data collection system. A block randomization scheme with no subgroups will be used for each center participating in the trial. Blocks will use randomly permuted sizes of even numbers only, consisting of an equal number of treatments in each block. The order of the treatment assignments in each block is random. Along with treatment allocation, each patient randomized is assigned an individual study number.

### **Surgical Treatment**

All patients will be treated with open reduction and internal fixation consisting of an intramedullary nail prior to their staged bone grafting procedure. Prior placement of a PMMA antibiotic spacer may be performed at the discretion of the surgeon to temporarily occupy the tibia fracture defect site and preserve space for the bone graft (these are to be removed prior to the bone grafting procedure).

The use of a PMMA spacers at the time of the initial injury is at the discretion of the surgeon. It will be recorded in the case report form. Antibiotic PMMA spacers may be used if there is a significant area of tissue and bone defect in a contaminated wound

Patients in the control group will receive the standard of care, cancellous autogenous bone graft harvested from the iliac crest using a standard surgical technique. Patients in the investigational treatment group will receive one INFUSE Bone Graft Large II kit (12 mg) in combination with freeze-dried cancellous allograft bone chips. Regardless of treatment assignment, the grafting material will be surgically implanted between 6 and 16 weeks after initial injury.

### **Autogenous Bone Graft Preparation**

For the autograft group, autogenous bone graft will be harvested from the iliac crest in the standard surgical fashion. If the recipient fracture site is free of infection, we will prepare the recipient site to expose bleeding bone. The approach chosen by the surgeon will be an anterior or posterior approach depending on the position of the fracture defect and the condition of the surrounding soft tissues. The autograft will be implanted within the fracture defect and to fill the fracture defect and along the proximal and distal margin.

### **INFUSE Bone Graft Preparation**

## IRB00003098 Funding Protocol rhBMP-2/ACS vs. Autograft for Critical Size Tibial Defects

The INFUSE Bone Graft should be prepared according to the manufacturer's instructions listed on the product; briefly 8.4 mL of Sterile Water for Injection is mixed to reconstitute the rhBMP-2 to a concentration of 1.50 mg/mL, 8.0 mL of this rhBMP-2 solution is then uniformly distributed onto the 3" by 4" bovine collagen sponge supplied in the kit, allow the wetted collagen sponges to stand for a minimum of 15 minutes before implantation.

### Bone Grafting Procedure

Up to 60 cc of bone graft (cancellous autograft bone or allograft bone) will be used to fill the tibia fracture defect. The grafting approach should be selected according to the position of the fracture and the condition of the surrounding soft tissues. Either an anterior or posterior approach is acceptable as long as the graft is placed in an area surrounded by a viable muscle mass. The proximal and distal margins of the defect site may be roughened with a burr or osteotome to expose bleeding bone. The bone graft is applied in and around the area surrounding the defect site until the defect is full. For the investigational patients, the INFUSE Bone Graft will be applied as an overlay after the defect has been first filled with cancellous allograft bone chips, the collagen sponge should bridge from proximal to distal end and cover the defect as much as possible based on the surgical opening.

### Duration/Follow-up Schedule

It is anticipated that the required patients will be enrolled into this study during an 18-month period and will be followed for one year. Thus, the data collection time is anticipated to be a 2.5 year period. The patients will be evaluated at 2 weeks, 6 weeks, 12 weeks, 18 weeks, 6 months and 12 months according to the following schedule:

Follow-Up Schedule	Process	Data Collected
Enrollment	Clinical examination	Inclusion/Exclusion criteria, patient characteristics, fracture characteristics, surgical summary, VAS
2 weeks	Clinical examination, functional outcomes	Clinical follow-up data, VAS
6 weeks	Clinical examination, functional outcomes, radiographs	Clinical follow-up data, VAS
12 weeks	Clinical examination, functional outcomes, radiographs	Clinical follow-up data, VAS
18 weeks	Clinical examination, functional outcomes, radiographs	Clinical follow-up data, VAS
6 months	Clinical examination, functional outcomes, radiographs	Clinical follow-up data, VAS, SF12, SMFA
12 months	Clinical examination, functional outcomes, radiographs	Clinical follow-up data, VAS, SF12, SMFA

## **Measurements**

Effectiveness Evaluation (x-ray, weight bearing, 2nd procedures)

Outcome measures will be “radiographic union,” “clinical union”, “wound healing and infection,” and “need for further intervention.”

Pain-will be documented using the Visual Analogue Scale (VAS) at each visit.

Short Form-12 (SF-12), Short Musculoskeletal Functional Assessment (SMFA) will be completed at 6 months and 12 months.

The **SF-12** questionnaire was developed from the Medical Outcomes Study. It is a self-administered, 12-item questionnaire that measures health-related quality of life in 8 domains. Both physical and mental summary scores can be obtained. Each domain is scored separately from 0 (lowest level) to 100 (highest level). The instrument has been extensively validated and has demonstrated good construct validity, high internal consistency, and high test-retest reliability. Our decision to use the SF-12 over other available instruments was based on its widespread use in orthopaedics, its use in previous studies evaluating fracture outcomes, and the strong evidence of validity.

The **SMFA** is a shorter version of the 101 item Musculoskeletal Function Assessment (MFA) questionnaire. The SMFA is a 46 item questionnaire consisting of the dysfunction and bother index. The dysfunction index has 34 items for assessment of patient function, while the bother index consists of 12 items designed to detect how much patients are bothered by functional items. The SMFA has been evaluated for reliability, validity and responsiveness in patient populations. We chose this scale because it is a short, validated instrument to provide us with information regarding the patient’s functional status.

Safety Evaluation (complications, re-operations, adverse events)

### Wound Complications

- Deep infections are defined as those that occur within one year from the procedure, involve deep soft tissue and that meet at least one of the following criteria: “purulent draining, a deep incision that spontaneously dehisces or is deliberately opened by a surgeon when the patient has at least one of the following signs or symptoms: fever (>38 degrees C), localized pain or tenderness, unless the incision is culture negative; an abscess or other evidence of infection involving the deep incision is found on direct examination, during reoperation, or by histopathology or radiologic examination; or diagnosis of a deep incisional SSI by a surgeon or attending physician” or require operative treatment.. All treatment and interventions will be recorded.
- Superficial infections are defined as those that occur within 30 days after the operative procedure and involve only skin or subcutaneous tissue of the incision and at least one of the following: purulent drainage from the superficial incision; organisms isolated from an

## **IRB00003098 Funding Protocol rhBMP-2/ACS vs. Autograft for Critical Size Tibial Defects**

aseptically obtained culture of fluid or tissue from the superficial incision; at least one of the following signs or symptoms of infection- pain or tenderness, localized swelling, redness or heat and the superficial incision is deliberately opened by surgeon unless the incision is culture=negative; or diagnosis of superficial incisional SSI by the surgeon or attending physician” and that are treated only with local antibiotics and wound care, and no operative treatment for the infection (Horan TC et al, 1992).

Swelling: Swelling will be defined as the absence of skin wrinkling.

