**A. INVESTIGATIONAL PLAN**

**Purpose**

Fractures of long bones constitute the majority of emergency operating room procedures in most trauma centers. Of these long bone injuries, tibial fractures are the most common. The National Center for Health Statistics reports an annual incidence of 492,000 fractures of the tibia and fibula per year in the United States. Patients with tibial fractures remain in the hospital for a total of 569,000 hospital days and incur 825,000 physician visits per year in the United States. Delayed fracture healing is a common complication associated with high-energy tibia fractures. Open tibia fractures with bone loss rarely unite without a secondary intervention. Delayed bone grafting of the defect is commonly used to provide stimulus for healing. The use of an autogenous iliac crest bone graft (ICBG) has remained the gold standard in the treatment of tibial non-unions with a bone defect. However, there are significant limitations to autogenous bone grafting, including the increased risk of infection from a second surgical incision and pain associated with the bone graft harvest site, which may range from 1-5 days to more than a year. Additional risks include iatrogenic fracture and damage to neurovascular structures. Also, not all patients are suitable donors. Relative contraindications to ICBGs include previous iliac crest harvesting; poor bone quality secondary to underlying disease, smoking or medications that affect the quality of bone; and advanced patient age. Finally, there is a finite amount of bone that may be obtained from the ilium, and it may not be adequate in all donors to address critical size defects. Recent technological advances with the advent of recombinant bone morphogenetic proteins emerging as a viable bone graft substitute may offer a viable alternative for patients.

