## **IRB00003098 Funding Protocol rhBMP-2/ACS vs. Autograft for Critical Size Tibial Defects**

*Null hypothesis: rhBMP-2/ACS has the same union rate when used in critical-sized defects as does ICBG.*

*Secondary:*

What is the relative effect of rhBMP-2 versus autogenous ICBG on infection rates in patients with nonunion or critical size defects following tibial shaft fractures?

*Null hypothesis #2: The infection rate in open tibias with critical-sized defects treated with rhBMP-2 and autogenous ICBG are the same.*

What is the economic impact of the use of RhBMP 2 for tibial fractures with critical sized defects?

*Null hypothesis #3: There will be no difference in the economic cost of the treatment of critical sized defects using the RhBMP-2 versus iliac crest bone graft.*

This investigation is a prospective, stratified, parallel, randomized, blinded multicenter trial to evaluate the use of rhBMP-2/ACS in 25 patients versus a control group of 25 patients who have tibial fractures with critical size defects. A committee of orthopaedic surgeons will independently adjudicate our primary outcome, fracture healing at 12 months. Participating centers are part of the Major Extremity Research Consortium (METRC) and have experience with performing randomized clinical trials. Approval by each center's institutional review board will be obtained prior to commencing the study and we will follow the research guidelines set forth by each site.

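### The infection definitions leave some skin-level infections in neither class, partly according to the treatment given, and do not carry over the tibial restriction of null hypothesis #2

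*Combined protocol and SAP*

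**What the plan says.** Infection is a secondary question with its own null hypothesis. The question asks "What is the relative effect of rhBMP-2 versus autogenous ICBG on infection rates in patients with nonunion or critical size defects". The paired null hypothesis #2 reads "The infection rate in open tibias with critical-sized defects treated with rhBMP-2 and autogenous ICBG are the same".

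The Wound Complications section, which continues over a page break, defines two classes:

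- **Deep:** "Deep infections are defined as those that occur within one year from the procedure, involve deep soft tissue and that meet at least one" of a list of criteria. After the list comes a further clause, "or require operative treatment".
- **Superficial:** "Superficial infections are defined as those that occur within 30 days after the operative procedure and involve only skin or subcutaneous tissue of the incision". At least one listed sign or diagnosis is also needed, and the event must be one of those "that are treated only with local antibiotics and wound care, and no operative treatment for the infection".

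There is no third class. Neither definition names the tibia, the recipient site or the iliac crest. The Purpose section counts among the drawbacks of autograft "the increased risk of infection from a second surgical incision", and Risks Associated with Standard Treatment lists infection as a risk of harvest. Only the control arm has a harvest incision (Autogenous Bone Graft Preparation). The Final Analysis section plans Fisher's exact test for categorical outcomes.

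**The concern.** Two things look wrong.

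First, the superficial definition adds a treatment condition to the tissue and time conditions, joined by an and. An infection of the skin that is given oral or intravenous antibiotics fails that condition, and without deep tissue involvement it does not become deep. The operating surgeon necessarily knows whether an iliac crest was harvested. The independent adjudication described is for the primary outcome, and the blinded assessment under Fracture Healing is radiographic; no blinded classification of infection is described. An arm-aware treatment decision can therefore settle whether an event counts.

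Second, null hypothesis #2 speaks of open tibias, while the paired question speaks of patients and the definitions speak of a procedure and an incision. Controls have two incisions and the rhBMP-2 arm has one. If donor-site infections were counted, the comparison would no longer answer a question about the tibia.

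At stake is whether the reported infection rates mean the same thing in both arms. With about 25 patients per arm, a handful of events decides how those rates look.

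**Working it through.** The plan gives no infection rate, power or sample size to reproduce; the Sample Size Justification concerns union only. The first check is therefore a reading of the definitions, and the arithmetic that follows is illustration.

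**Step 1: are the classes exhaustive?** The operative clause at the end of the deep definition can be read two ways: (A) as one more criterion, with deep tissue still required, or (B) as a separate route into the deep class.

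| Infection | Superficial? | Deep, reading A? | Deep, reading B? |
|---|---|---|---|
| Skin-level, within 30 days, local antibiotics and wound care only | Yes | No | No |
| Skin-level, within 30 days, systemic antibiotics, no operation | No (treatment condition) | No (tissue) | No (no operation) |
| Skin-level, after day 30, no operation | No (window) | No (tissue) | No (no operation) |
| Skin-level, within 30 days, operated on | No (treatment condition) | No (tissue) | Yes |

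Rows two and three fall in neither class on both readings. Row four depends on the reading.

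**Step 2: is the site defined?** The words about open tibias in null hypothesis #2 may restrict the endpoint or merely describe the population. The definitions repeat no site. Nothing in the text available says where an iliac crest infection belongs.

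**Step 3: size per event.** With 25 patients per arm, 1/25 = 4 percentage points.

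**Step 4: unclassified infections (assumed rates).** Suppose 6 of 25 patients in each arm have a tibial infection, and in one arm two of these are skin-level and given systemic antibiotics. The counted rates are 6/25 = 24% and (6 − 2)/25 = 16%, a difference of 8 points that comes from the rule. If instead the same share is unclassified in both arms, the cost is power. With true rates of 10% v 30%, exact power of the two-sided Fisher test at 0.05 is about 30% with all infections classified, 22% with 20% unclassified (rates 8% v 24%) and 12% with 40% unclassified (6% v 18%).

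**Step 5: donor-site infections, if counted (assumed rates).** Let t be the tibial rate, equal in both arms, and d the donor-site rate in controls, independent of t. The any-site control rate is 1 − (1 − t)(1 − d), which exceeds t by d(1 − t).

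- Smallest excess over t = 10–30% and d = 2–10%: 0.02 × 0.70 = 1.4 points.
- Largest excess: 0.10 × 0.90 = 9.0 points.
- Chance of at least one donor-site infection in 25 controls, 1 − (1 − d)^25: 40%, 72% and 93% for d = 2%, 5% and 10%.

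The chance that the Fisher test rejects with no tibial difference rises from 0.9% to 7.1% at t = 10%, d = 10%, and from 2.2% to 5.2% at t = 20%, d = 10%. In the other seven combinations with t = 10%, 20% or 30% and d = 2%, 5% or 10%, it stays below 5%.

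In counts, 4/25 = 16% in each arm plus one or two donor-site infections in other controls gives 5/25 = 20% or 6/25 = 24% v 16%. The two-sided Fisher p-values are 1.00 and 0.73.

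**The case against.** The strongest reply is that the tibia is already the natural reading. Null hypothesis #2 names it, and Steps to Minimize Risk ties the infection check at each visit to the injured limb. A reader might infer that the plan directs the two wounds to be pooled. It does not: the definitions are silent on site, so pooling is possible but not prescribed.

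A reader might also infer that leaving donor-site infections out would hide a harm of harvest. The documents do not support that. The adverse-event section covers any adverse event from implantation onward, whether or not it is thought implant-related, and provides for annual and final reports. The safety evaluation covers complications, and the monitoring board compares adverse-event rates by group.

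Nor are unclassified infections lost as data. Wound Complications requires all treatment to be recorded, and the documents never say that the endpoint is exactly the sum of the two classes. This stands, but it does not close the gap: recorded events still need a rule that says which of them count, and that rule should exist before results are seen.

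The 30-day window could be taken for an error. The text attributes the superficial definition to a published surveillance source, so the window is a convention and can stay as a class. What is missing is a place for later events.

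Finally, every rate in the illustrations is assumed, and in the simple count example the planned test would conclude nothing different. That is correct. The point concerns what the reported rates mean more than the test result. The case report form is not among the documents, so it may already record the site.

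**Conclusion.** The point holds in a limited form and should be addressed. On the text as written, two kinds of skin-level infection fall in neither class: those given systemic antibiotics without operation, and those that start after day 30 and are not operated on. For the first kind, the treatment chosen by a surgeon who knows the arm decides whether the event counts. The comparison for null hypothesis #2 can therefore undercount infections, and it could do so unequally; nothing in the documents shows that it will.

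The site question is an ambiguity to close. It is not a demonstrated bias, and the illustrative 4- to 8-point control excess from donor-site events should not be read as an expected result. The only figure that rests on the plan's own numbers is 4 points per event in an arm of 25. The endpoint is secondary and unpowered, and the primary union analysis is untouched.

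**What to change.** 1. Delete the treatment condition from the superficial definition. Classify depth by the tissue involved, and record treatment, including any operation, as a separate item. This also removes the two readings of the operative clause.
2. State that the endpoint for null hypothesis #2 is infection at the tibial graft site, superficial or deep, from graft surgery through 12 months.
3. Keep the 30-day superficial class, and tabulate later superficial tibial infections beside it so that none drops out of the total.
4. Report donor-site infections on a separate line.

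This takes a few lines in the definitions and, if the case report form does not already have one, a field for infection site. The rates become slightly less comparable with series that use the cited surveillance definition; keeping the 30-day class limits that loss. No treatment or visit changes.
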